28 usual care in ruling out patients without significantly obstructive CAD before invasive catheterization and
29 improving clinical prognosis during follow-up in a randomized design.

30 **Method/design**

[figure not shown]
31 **Study aim**

32 TARGET trial is a multicenter, prospective, open-label, and pragmatic randomized controlled trial
33 evaluating the effect of a CCTA/CT-FFR strategy (group A) on management decision making versus usual
34 care (group B) in intermediate-to-high risk patients with suspected CAD who undergo clinically indicated
35 diagnostic evaluation. Recruitment commenced in August 2019. The schedule of enrollment and
36 assessments follows the SPIRIT Figure. The study protocol (Version 3.0/201812) and other relevant
37 documentations have been approved by the institutional human research ethic committee of Chinese PLA

38 General Hospital and the relevant national ethics committees as well as registered on ClinicalTrials.gov
39 identifier: NCT03901326.

40 **Setting**

41 This multicenter randomized controlled clinical trial will be carried out in 6 tertiary hospitals across China,
42 all of which has the volume of over 200 patients in outpatient area of cardiology division each working day.
43 Participating subjects will be enrolled and subsequently assigned to either usual care group or CT-FFR care
44 group via computer-generated random numbers (1:1 ratio) (Figure 1). The trial accords with the SPIRIT
45 guidelines. The treatments (both intervention and control) will be delivered by licensed clinicians in the
46 participating sites. Central telephone is used for allocation of sequence. Participants will be randomized to
47 the CT-FFR examination group or usual care group using a randomization procedure. The cardiologist will
48 be aware of patients' group allocation because they will provide the trial intervention, but they will not be
49 involved in the analysis. Participants are not blind to their group allocation, nor are their physicians who are
50 informed of screening results of their patients (if the patient consents) and give the recommendation by
51 outpatient or telephone. There will be no special criteria for discontinuing or modifying allocated
52 interventions.

53

54 **Figure 1: The flow chart of TARGET trial.**

55

56 **Eligibility criteria**

57 **Inclusion criteria**

58 Consecutive patients with new-onset chest pain suspicious for CAD will be included. Subjects with

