163 Trials (SPIRIT) Figure)

164

165 The data were collected, coded, and entered by the trial investigators, and the paper-based CRF form
166 is sent to the trial office by investigators to ensure that the data would not be tampered. The researchers
167 used double data entry and range checks for data value method to ensure the accuracy of the data. A
168 clinical research organization (CRO) has been contracted to oversee the monitoring of all sites,
169 establishing the eCRF and checking the completeness and consistency of the trial data. Adherence to this
170 trial will be monitored via hospital information system. The follow-up examination results should be sent
171 to the research site, and the examination results of the grade 3 hospital can be accepted to maintain the
172 credibility.

173 **Endpoint of the study**

174 The primary endpoint of the present trial is comparison between the two arms in the rate of planned ICA
175 without significant obstructive CAD or interventions within 90 days. Significant obstructive CAD is
176 defined as more than or equal to 70% of diameter stenosis by quantitative coronary analysis in core lab or
177 invasive FFR ≤ 0.8 if available during procedure. Interventions includes stent implantation, balloon
178 dilation and bypass surgery.

179 The secondary endpoint will be the comparison between the two treatment arms in terms of MACE,
180 quality of life, cumulative effect dose of radiation exposure, and overall cardiac medical cost during the
181 follow-up at 1 year.

183 The Seattle Angina Questionnaire (SAQ-7) was used to assess the clinical effect and quality of life
184 (QOL). We will also measure the cumulative radiation exposure dose (ED) over the entire study period by
185 assessing the original average dose for each test performed during the follow-up. In case the ED for each
186 test is not known, we will use the standard ED available for each test in the literature.

187 Major adverse cardiovascular events (MACE) will be defined as a combined endpoint of (a)
188 hospitalization for unstable angina, (b) revascularization by PCI or CABG after 90 days, (c) non-fatal MI,
189 and (d) cardiac death: any death because of immediate cardiac cause (e.g., MI, low- output failure, fatal
190 arrhythmia) or vascular cause (e.g., cerebrovascular disease, pulmonary embolism, ruptured aortic
191 aneurysm, dissecting aneurysm, or other vascular cause). Unwitnessed death and death of unknown cause

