245 during ICA in usual care group is about 30%. The frequency of reduction in the primary endpoint is
246 expected to be 30% for a \geq 90% power. Considering a drop-off up to 10%, the final overall population
247 should be of 1216 patients.

248 **Statistical analysis plan**

249 Baseline characteristics will be presented. Continuous variables were described as mean \pm Standard
250 deviation (SD) or median (interquartile range), and compared between the groups using either Student's 2
251 sample t- test for paired or nonparametric Wilcoxon rank sum test. Categorical variables were summarized as
252 counts (percentages) and compared using the Pearson chi-square test or Fisher exact test if cell frequencies

253 were insufficient. Kaplan-Meier survival curves and Cox-regression modelling will be used for time to event
254 outcomes. The patient reported outcomes, such as Seattle Angina Questionnaire, will be compared between
255 the two groups using 2 sample t-test. The total cardiac costs will be compared using nonparametric Wilcoxon
256 rank-sum test) or a 2 sample t-test based on means of log transformed costs between the two groups, because
257 of the expected skew in cost data. The hazard ratio (HR) is presented as 95% confidence intervals (CI). P <
258 0.05 is considered as significance in statistics. Because there are no anticipated problems that are detrimental
259 to the participants, interim analyses and formal stopping procedure are not necessary for this trial. Missing
260 values will be managed by using multiple imputation. If there is any non-adherence with the trial protocol
261 and intervention plan, investigators will record it truthfully. Intention-to-treat analysis will be applied for
262 patients who do not adhere to the intervention. In addition, all efficacy analyses were performed on a
263 per-protocol set that excluded patients with major protocol deviations. Based on the data of the current study,
264 further subgroup analysis will be conducted for the additional purpose in the future.

265

266 **Analysis and reporting Plan**

267 **1. Disposition of the study population**

268 A clear account of all patients who entered the trial will be produced. Withdrawal information including
269 the primary reasons of discontinuation will be summarised and presented by group.

270 **2. Protocol deviations**

271 A listing of all Major or Potential/Serious Breach (Major protocol deviations with potential to affect

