272 patient safety/data) and Potential/Serious Breach (Major, Potential or Serious Breach of GCP guidelines or
273 consistent non-compliance by site) will be produced (by patient and site where applicable).

274 **3. Baseline and demographic characteristics and Treatment information (ITT population)**

275 Summary statistics will be produced and presented by group for demographic and baseline
276 characteristics, comparisons will be undertaken to investigate clinical importance of any imbalance.

277 **4. Primary outcome (ITT population)**

278 The primary endpoint of the present trial is comparison between the two arms in the rate of ICA
279 without significant obstructive CAD or intervention within 90 days. The significant obstructive CAD is
280 defined as more than or equal to 70% DS by quantitative coronary analysis or invasive FFR \leq 0.8, if
281 available during the procedure. Intervention includes stent implantation, balloon dilation and bypass
282 surgery. This result will be showed by a Figure.

283 **5. Secondary outcome: clinical outcomes (ITT population and PP population)**

284 For the comparison of clinical outcomes between the two groups at 1 year. The number and
285 proportion of experiencing at least one event, including: (a) hospitalization for unstable angina, (b)
286 revascularization by PCI or CABG after 90 days, (c) non-fatal MI, and (d) cardiac death: any death
287 because of immediate cardiac cause) will be reported and presented by group. Time to the first clinical
288 event will be described using Kaplan Meier plots, presented by arm, and analysed using Cox regression

289 modelling.

290 **6. Secondary outcome: medical cost outcomes (ITT population)**

291 Total medical costs over 12 months of follow-up will be measured for each patient by sum of the
292 numbers of key medical resources used between study entry and the 12 months follow-up point. The
293 CT-FFR assessment is free during the trial, but the cost of CT-FFR will be add in the analysis based on a
294 uniform market price once obtained. The total cardiac medical costs over follow-up will be compared
295 between the two arms in an intention-to-treat fashion. The mean and median cost should be presented and
296 compared in the two randomly assigned groups. The total cardiac cost was compared using a two-sample
297 t-test after a log transformation if skew distribution of the data was found. If the distribution remains

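### The secondary endpoints share one P < 0.05 rule with no hierarchy, gate on the primary, alpha control or exploratory label, although prognosis is part of the stated purpose

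*Combined protocol and SAP*

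**What the plan says.** The Endpoint of the study section names one primary endpoint, the 90-day rate of planned ICA without obstructive disease or intervention. It then says "The secondary endpoint will be the comparison between the two treatment arms in terms of MACE", followed by "quality of life, cumulative effect dose of radiation exposure, and overall cardiac medical cost during the" one-year follow-up. That makes four secondary endpoints, each framed as a between-arm comparison.

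The Statistical analysis plan sets one threshold: P < "0.05 is considered as significance in statistics". It does not say whether tests are one- or two-sided. It rules out interim analyses, and it announces that "further subgroup analysis will be conducted for the additional purpose in the future".

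The Analysis and reporting Plan treats the secondaries as follows:

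- **MACE** (section 5, headed "Secondary outcome: clinical outcomes (ITT population and PP population"): time to first event "event will be described using Kaplan Meier plots, presented by arm, and analysed using Cox regression" modelling.
- **Cost** (section 6): t-test on log costs, or a rank test if skewness remains, framed as a test of hypotheses.
- **SAQ-7** (section 7): t-test or Wilcoxon rank-sum test on change scores.
- **Radiation dose** (section 8): to be reported; no test is named.

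The exploratory label appears only in section 10, for the drivers of the revascularization rate. That is also the only analysis made conditional on the primary result.

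The Background closes with the study purpose, which is to evaluate whether CCTA/CT-FFR does better than usual care both in ruling out patients before catheterization and in "improving clinical prognosis during follow-up in a randomized design".

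**The concern.** Only the first half of that purpose is carried by the primary endpoint. The second half, prognosis, rests on a secondary test, and the plan does not say what a significant or non-significant result on that test allows the trial to conclude.

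Two situations are left open. If the primary fails, a P value below 0.05 for MACE, SAQ-7, cost or dose could be reported as a benefit of CT-FFR and still comply with the plan. If the primary succeeds, any one of several tests at the full 0.05 could support a second claim. MACE has a further ambiguity: it is analysed in both the ITT and the per-protocol set, and no passage says which decides. It is also the secondary result most likely to influence practice.

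**Working it through.** **Is there a figure to reproduce?** No. The only error-rate figure in the documents is the per-test 0.05. No familywise rate is stated for the secondaries, so the check is to find the rate that the plan's rule implies.

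**Inputs from the documents.** Per-test alpha is 0.05. Four secondary comparisons are listed, of which three (MACE, SAQ-7, cost) have a named test. There are no interim looks.

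**Assumptions.** Tests are two-sided, consistent with the planned 95% confidence interval for the hazard ratio. Test statistics are approximately normal with a common correlation ρ. The documents give no correlation between endpoints, so the range 0 to 0.8 is shown.

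**Independent tests.** The chance of at least one false positive among k true nulls is 1 − 0.95^k:

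- k = 2: 1 − 0.9025 = 9.75%
- k = 3: 1 − 0.8574 = 14.3%
- k = 4: 1 − 0.8145 = 18.5%

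**Correlated tests.** Write each statistic as √ρ·U + √(1−ρ)·E, with U shared and E independent, both standard normal. Given U = u, the chance that one statistic stays within ±1.96 is Φ((1.96 − √ρ·u)/√(1−ρ)) − Φ((−1.96 − √ρ·u)/√(1−ρ)). Raise this to the power k, average over u, and subtract from 1. Numerical integration gives the following; simulation agrees to about 0.1 percentage point.

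| True nulls | ρ = 0 | ρ = 0.5 | ρ = 0.8 |
|---|---|---|---|
| 4 (all secondaries) | 18.5% | 15.6% | 11.4% |
| 3 (those with a named test) | 14.3% | 12.5% | 9.8% |
| 2 (MACE and SAQ-7 only) | 9.75% | 9.1% | 7.8% |

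Relative to 0.05, that is 2.3 to 3.7 times for four tests, 2.0 to 2.9 times for three, and 1.6 to 1.95 times for two.

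**Errors favouring CT-FFR only.** Counting one direction, against a nominal 2.5% for a single test:

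- four tests: 9.6% (ρ = 0), 7.8% (0.5), 5.7% (0.8)
- three tests: 7.3%, 6.3%, 4.9%

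The absolute risk is about half of the table above; the ratio to nominal is almost the same.

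**MACE from either analysis set.** If a significant MACE result could be taken from ITT or per-protocol, the same formula with k = 2 and an assumed correlation of 0.95 between the two statistics gives about 6.5% instead of 5.0% (7.0% at 0.90, 5.9% at 0.98). This is a small addition.

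**Check on the remedy.** With four true nulls, Holm makes an error only if the smallest P value is at or below 0.05/4 = 0.0125. For independent tests the rate is 1 − 0.9875^4 = 4.9%; at ρ = 0.5 it is 4.3%.

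**The case against.** Secondary endpoints are often tested without adjustment and read as supportive. On that view the plan breaks no rule of its own: 0.05 is a per-test threshold, each test delivers it, and no familywise rate is promised. This stands. What is missing is a statement of the secondaries' inferential status, and the point does not show that the plan's stated error rate is wrong.

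Several stronger readings are tempting, and the documents do not support them.

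- **That all four endpoints are definitely tested.** Section 8 only says that dose will be reported. A test follows only from its being listed as a comparison under Endpoint of the study, or from the general sentence on continuous variables, which comes directly after the baseline sentence.
- **That the inflation is one fixed multiple of alpha.** About three times needs four tests, every null true, and a correlation near 0.5 that no document gives.
- **That every null is plausibly true.** Cost and dose are tied to the number of angiograms, so if the primary effect is real they are unlikely to be null. The two-null row, about 8% to 10%, then describes the risk better.
- **That the trial sets out to show better prognosis.** The Background says evaluate whether, the Study aim section concerns management decisions and does not mention prognosis, and the sample size rests on the primary endpoint alone.

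The per-protocol set is introduced as an addition to ITT, so main versus supportive is a natural reading, although it is not explicit. The subgroup sentence concerns future work and adds little.

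What survives is that the supportive reading is nowhere written down. Section 10 shows that the plan does use gating and an exploratory label for one other analysis, but not for the secondaries, while the stated purpose includes prognosis.

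**Conclusion.** The point holds as a gap in the plan that is cheap to close. The secondary comparisons share one 0.05 rule with no order, gate, adjustment or label, so the plan permits a secondary benefit claim whatever the primary shows.

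If all nulls are true, the chance of at least one false-positive secondary result in either direction is about 10% to 14% over the three endpoints with a named test, and 11% to 19% if dose is tested too. Errors favouring CT-FFR are about half of that. If cost and dose truly differ, the figure for MACE and SAQ-7 is about 8% to 10%. These ranges rest on two-sided tests and an assumed common correlation between 0.8 and 0.

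A reader might infer that the trial's main conclusion is at risk. It is not: there is one primary comparison, in the ITT population, with no interim look, and its alpha is untouched.

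**What to change.** Add to the Statistical analysis plan:

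> The only confirmatory test is the primary endpoint in the ITT population at two-sided 0.05. If it is significant, MACE, SAQ-7, cumulative radiation dose and total cardiac cost (ITT) are tested by the Holm procedure at overall two-sided 0.05. If it is not significant, they are reported as estimates with 95% confidence intervals and no significance claim. Per-protocol and subgroup results are supportive or exploratory.

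For this to work, section 8 must name a test for dose. Sections 6 and 7, which refer to both nine and 12 months for cost and SAQ-7, must settle on one time point.

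An acceptable alternative is to label all four secondaries exploratory, report them as estimates with 95% confidence intervals, and word the prognosis aim as exploratory.

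The cost is wording only, with no extra patients or data. There is a small downside either way. Under Holm, the smallest secondary P value must be at or below 0.0125. Under the label-only version, no secondary result can be claimed as confirmed.

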140 relevant data with people from the hospital taking part in the research, where relevant. This trial does not
141 involve collecting biological specimens for storage.

142 **Downstream decision making**

143 The results of the index test will be provided to the reference cardiologist of the patients’ institution who
144 will make clinical decisions based on the integrated evaluation of patient clinical assessment and index
145 test findings. Optional use of invasive FFR or intravascular imaging (IVUS or OCT) and the decision on
146 the mode of revascularization are left to the interventional cardiologists and depends on local practice
147 standard.

148 At baseline, 6 months, and 12 months, recommendations for therapy are made in line with guidelines
149 published. The goal of anti-hypertensive therapy is to achieve a blood pressure of less than 140/90 mmHg.
150 The choice of anti-hypertensive therapy will be left to the treating physician. The aim of anti-lipid therapy
151 is to achieve levels of LDL $< 1.9\text{mmol/l}$. In the first instance, statin therapy will be initiated and then
152 increased with the addition of a second agent if necessary. In the case of diabetics with a raised blood
153 sugar, the primary health care physician is asked to measure HbA1c and to ensure that the patients’
154 subsequent therapy is tailored to achieve a HbA1c of less than 6.5mg/dl. Smokers are referred to the

155 smoking cessation clinic.

156 **Follow-up**

157 Subjects will be contacted regularly by trained interviewers at 90 days, 3 months, 6 months, and 12
158 months post-enrollment for follow-up assessment until death, withdrawal, or end of the trial (**Figure 3**).

159 All subjects are followed for a minimum of 12 months. An independent clinical event adjudication
160 committee (CEC) reviewed all primary endpoint event and secondary endpoints in a blinded fashion. The
161 decisions of CEC will be used to implement the final statistical analysis.

Time point	STUDY PERIOD					
	Enrollment visit	Allocation	Intervention	3months± 7days	6months ± 7days	1 year ± 7days
Eligibility screen	×					
Informed consent	×					
Demographic data	×					
Allocation		×				
Diagnosis			×			
Conventional Coronary Angiography			×	×		
Coronary revascularization			×	×	×	×
MACE				×	×	×
AE				×	×	×
Medical cost				×	×	×
Quality of life				×	×	×
Radiation exposure				×	×	×

162 **Figure 3:** Chronology of the research (Standard Protocol Items: Recommendations for Interventional

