298 right-skewed after log transformation, a non-parametric Mann-Whitney tests will be needed to test the
299 hypotheses that nine month costs differ between groups.

300 **7. Secondary outcome: patient reporting outcome (ITT population)**

301 For the questionnaire patient reported endpoints (Seattle Angina questionnaire-7) at 12 months, change
302 scores from baseline to 12 months will be presented and mean (or median) change from baseline to 9
303 months will be compared between groups using t-tests (or the Wilcoxon rank-sum test), where
304 appropriate.

305 **8. Secondary outcome: radiation exposure outcome (ITT population)**

306 The cumulative radiation exposure dose (ED) over the entire study period will be reported by
307 assessing the original average dose for each test performed during the follow-up. In case the ED for each
308 test is not known, we will use the standard ED available for each test in the literature.

309 **9. Safety reporting (ITT population and PP population)**

310 CCTA related serious adverse events will be recorded and summarized if any. A listing of serious
311 adverse events will be provided for all related/unrelated SAEs.

312 **10. Other analyses (ITT population and PP population)**

313 If differences on the primary outcome are observed between groups, exploratory analyses into
314 revascularization rate to determine what the drivers are will be carried out. Some results of diagnostic
315 Strategy during initial management, as well as invasive coronary angiography, will be showed by tables
316 and.

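### SAQ-7 is to be analysed as change from baseline, but no SAQ-7 is scheduled before allocation; the schedule and SAP section 7 must be reconciled

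*Combined protocol and SAP*

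**What the plan says.** All places are in the combined protocol and SAP.

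- **Analysis and reporting Plan, section 7.** The result is a change score: "scores from baseline to 12 months will be presented and mean (or median) change from baseline to 9" months is the quantity tested, by t-test or Wilcoxon rank-sum test.
- **Follow-up, Figure 3.** The columns are "Enrollment visit Allocation Intervention 3months± 7days 6months ± 7days 1 year ± 7days". The row "Quality of life" is marked under the last three only.
- **Follow-up, text.** "Subjects will be contacted regularly by trained interviewers at 90 days, 3 months, 6 months, and 12" months after enrollment. No questionnaire at enrollment is mentioned.
- **Endpoint of the study.** Quality of life is a secondary endpoint, compared during follow-up at 1 year. The instrument is named without an assessment time: "The Seattle Angina Questionnaire (SAQ-7) was used to assess the clinical effect and quality of life".
- **Statistical analysis plan.** "The patient reported outcomes, such as Seattle Angina Questionnaire, will be compared between" the two groups by a two-sample t-test; change from baseline is not mentioned. For missing data, "values will be managed by using multiple imputation".
- **Setting.** The trial is open-label: "Participants are not blind to their group allocation, nor are their physicians who are" told of the results.

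**The concern.** A change score needs a starting value. Section 7 takes one for granted, and the schedule does not provide it. A site that works strictly from Figure 3 would reach the 1-year visit with three SAQ-7 scores per patient, all obtained after allocation and none usable as a baseline.

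At stake is the analysis of the only patient-reported instrument that the plan names. A score from before allocation cannot be obtained afterwards, so each patient enrolled without one stays without one. Recruitment began in August 2019 and the document is dated 20 August 2020, so some patients may already be in that position.

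**Working it through.** The plan gives no figure to reproduce here. The check is whether the analysis can be run on the scheduled data.

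1. **What section 7 needs.** A SAQ-7 before allocation and a SAQ-7 at the end point, per patient.
2. **What Figure 3 supplies.** Scores at 3 months, 6 months and 1 year. The enrollment column is marked for eligibility, consent and demographic data only. The quality-of-life row is blank at enrollment, allocation and intervention.
3. **Could the row be misread?** This is unlikely. Other rows carry marks in the early columns where one expects them: allocation under allocation, diagnosis under intervention, revascularization under intervention and all three follow-up visits. The quality-of-life row has the same pattern as MACE, adverse events, cost and radiation. Those accrue after randomisation and need no starting value.
4. **Does other text fill the gap?** No. The baseline mentioned under Downstream decision making concerns therapy recommendations. Section 3 of the Analysis and reporting Plan summarises baseline characteristics without naming SAQ-7.
5. **Can imputation supply it?** No, if nobody has the score. Multiple imputation needs observed values of the variable from which to model the missing ones.
6. **Can the 3-month score stand in?** No. It follows allocation, the index strategy and any early angiography or revascularization.
7. **Is the 9-month time point the whole problem?** No. No 9-month visit is scheduled either, so neither end of the tested contrast has a scheduled measurement. Changing 9 to 12 repairs the later end only.
8. **What remains computable?** The 1-year score in both arms. A comparison of 12-month scores between randomised arms needs no baseline to be valid, and it fits the wording of Endpoint of the study and of the Statistical analysis plan.

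**What a baseline would be worth.** Assume the same standard deviation at both times and a within-arm correlation r between baseline and 12 months. The document gives no r, so 0.3 to 0.7 is an assumed range. Standard errors of the between-arm difference, relative to 12-month scores alone, are:

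- change score: sqrt(2(1 − r))
- 12-month score adjusted for baseline: sqrt(1 − r²)

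| r | 12-month score alone | Change score | Adjusted 12-month score |
|---|---|---|---|
| 0.3 | 1 | sqrt(1.40) = 1.18 | sqrt(0.91) = 0.954 |
| 0.5 | 1 | sqrt(1.00) = 1.00 | sqrt(0.75) = 0.866 |
| 0.7 | 1 | sqrt(0.60) = 0.77 | sqrt(0.51) = 0.714 |

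Adjustment reduces the standard error by 1 − 0.954 = 0.046 (about 5%) to 1 − 0.714 = 0.286 (about 29%). The change score that the plan specifies is less precise than the 12-month score alone when r is below 0.5.

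**The case against.** The strongest reply is that Figure 3 is not a full list of data collected. Its enrollment column shows little beyond demographics. Yet the protocol makes therapy recommendations at baseline against blood pressure, LDL and HbA1c goals, none of which has a row, and section 3 of the Analysis and reporting Plan expects baseline characteristics as well as demographics. Section 7 itself presupposes a baseline SAQ-7. The case report form is not part of the document. An omission from the figure is therefore at least as plausible as a questionnaire that is never given. This stands: the document shows an inconsistency and does not show that the score is uncollected.

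Three stronger readings are tempting, and the document supports none of them.

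- *That the quality-of-life endpoint cannot be analysed.* Only the change score is affected, as step 8 of the working shows.
- *That sites will use a late or recalled baseline and so bias the result.* No text plans this. In an open-label trial such a value could be influenced by the arm, which is a reason to rule it out in advance and not a defect already in the plan.
- *That the missing baseline costs the planned analysis 5% to 29% in precision.* That range is the gain from a covariate-adjusted analysis, which the plan does not contain. For the planned change score the effect could go either way.

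It is also fair to say that this is one of four secondary outcomes, that it does not enter the sample size, and that the primary endpoint is untouched. What the reply does not remove is the mismatch: section 7 cannot be carried out on the schedule as written.

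**Conclusion.** The point holds as an internal inconsistency of moderate severity. If the schedule is followed exactly, the change-from-baseline SAQ-7 analysis cannot be computed in either arm, and imputation cannot rescue it. The 12-month comparison between arms can still be made.

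The conclusion rests on Figure 3 and the text alone. If the case report form already holds a SAQ-7 taken before allocation, the defect shrinks to a missing mark in the figure. The precision range rests on the assumed correlations and equal variances, and it measures what an adjusted analysis would gain.

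**What to change.** 1. **Figure 3.** Mark quality of life (SAQ-7) in the enrollment column, to be completed after consent and before allocation, in both arms. If it is already collected then, say so.
2. **Section 7, main comparison.** Make the all-randomised comparison the 12-month SAQ-7 score between arms, adjusted for the pre-allocation score if it is collected. Replace the 9-month time point with this scheduled visit.
3. **Section 7, missing baselines.** State the rule in advance, for example a missing-baseline indicator or multiple imputation. Imputation is an option only if some patients have an observed baseline.
4. **Patients already enrolled without a pre-allocation score.** Do not use a value obtained after allocation as their baseline. They enter the main comparison through the 12-month score. Show change scores only for patients with a true baseline, and label them as supplementary.

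The cost is one seven-item questionnaire at a visit that already takes place, one case report form page if none exists, and a short revision of section 7. The small downside is that patients enrolled earlier may contribute only a 12-month score, so the precision gain would be smaller than the range above suggests.

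### The SAQ-7 comparison is an unadjusted test on change scores and is not fixed in advance; a prespecified ANCOVA would be at least as precise, provided baseline SAQ-7 is collected

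*Combined protocol and SAP*

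**What the plan says.** Three places describe the SAQ-7 analysis or the data for it.

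- **Analysis and reporting Plan, item 7.** It is introduced as a 12-month endpoint: "For the questionnaire patient reported endpoints (Seattle Angina questionnaire-7) at 12 months, change" "scores from baseline to 12 months will be presented and mean (or median) change from baseline to 9" "months will be compared between groups using t-tests (or the Wilcoxon rank-sum test), where" appropriate. The 12-month change is thus presented, while the change that is tested runs to 9 months. No covariate is named, and no rule says when the rank test replaces the t-test.
- **Statistical analysis plan, general paragraph.** "The patient reported outcomes, such as Seattle Angina Questionnaire, will be compared between" the arms by a two-sample t-test. It does not say whether the variable is the follow-up score or the change, and it mentions no rank test. The only confidence interval in that paragraph is for the hazard ratio. For missing data it says that "values will be managed by using multiple imputation", with no imputation model.
- **Follow-up, text and Figure 3.** "Subjects will be contacted regularly by trained interviewers at 90 days, 3 months, 6 months, and 12" months. The row "Quality of life" is marked at 3 months, 6 months and 1 year. It is not marked at enrolment, allocation or intervention.

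Endpoint of the study lists quality of life among the secondary endpoints at 1 year. No SAQ-7 effect size, SD, correlation or power is given anywhere.

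**The concern.** There are two issues, both about method.

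First, the comparison is not pinned down. A t-test on the follow-up score, a t-test on change and a rank test on change can each be defended from the text. The rank test does not estimate a mean difference, so the choice alters what is reported as well as the p-value. Nothing settles it before the data are seen.

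Second, a raw change score is a wasteful use of a baseline. It subtracts the whole baseline value although the baseline predicts only part of the follow-up value. A chance baseline difference d between arms then enters the estimated effect as about −(1 − r)d (equal SDs). Item 3 of the Analysis and reporting Plan looks for baseline imbalance, but no SAQ-7 analysis adjusts for it.

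At stake is the width of the interval around a named secondary endpoint, and confidence that its test was not chosen after the fact.

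**Working it through.** The plan states no figure for SAQ-7, so there is none to reproduce. From the documents I use only the total of 1216, the 1:1 allocation and the 10% drop-off, to get patients per arm: 1216 × 0.9 / 2 ≈ 547. The correlation r and the SDs are assumptions, shown over a range.

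**1. Is ANCOVA ever worse?** Let s1 and s2 be the baseline and 12-month SDs. Per-patient variances:

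- change score: s1² + s2² − 2·r·s1·s2
- ANCOVA: s2²(1 − r²)
- difference: s1² − 2·r·s1·s2 + r²·s2² = (s1 − r·s2)²

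The difference is a square, so in large samples ANCOVA is never less precise, whatever r and the SDs are.

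**2. Size with equal SDs.** Change: 2(1 − r)s². ANCOVA: (1 − r²)s². Ratio: (1 + r)/2. Saving: (1 − r)/2. Against a t-test on the 12-month score alone, which the general paragraph also allows, the saving is r².

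| r | change / s² | ANCOVA / s² | saving vs change | saving vs 12-month score |
|---|---|---|---|---|
| 0.3 | 1.40 | 0.91 | 35% | 9% |
| 0.5 | 1.00 | 0.75 | 25% | 25% |
| 0.7 | 0.60 | 0.51 | 15% | 49% |

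Outside that range, the saving against change is 40% at r = 0.2 and 10% at r = 0.8.

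**3. Unequal SDs.** With k = s2/s1 the saving against change is (1 − r·k)² / (1 + k² − 2·r·k).

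| k | r = 0.3 | r = 0.5 | r = 0.7 |
|---|---|---|---|
| 0.6 | 67% | 65% | 65% |
| 0.8 | 50% | 43% | 37% |
| 1 | 35% | 25% | 15% |
| 1.25 | 22% | 11% | 2% |

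**4. What it means at this trial's size.** The detectable difference at 547 per arm, two-sided 0.05 (sidedness assumed), 80% power and equal SDs is (1.96 + 0.84) × √(2/547) × √(variance / s²), in SD units:

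- r = 0.3: 0.200 (change), 0.162 (ANCOVA)
- r = 0.5: 0.169, 0.147
- r = 0.7: 0.131, 0.121

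**5. What the 3- and 6-month scores would add.** I compared ANCOVA with a repeated-measures model that has a separate mean per arm and visit and adjusts for baseline. With complete data the variance of the 12-month contrast is identical (for example 0.75 s² in both at r = 0.5), so the gain is 0%. With 10% monotone dropout spread evenly over the visits and assumed correlations of 0.5 to 0.8 between follow-up scores, the gain over complete-case ANCOVA is about 1% to 4.5%. For example, at r = 0.5 and a follow-up correlation of 0.7, the variance is 0.810 s² against 0.75/0.9 = 0.833 s², a gain of 2.8%.

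**The case against.** The strongest reply is that nothing here is invalid. Under randomisation a t-test on change scores is unbiased, and chance imbalance costs precision without inflating type I error. The endpoint is secondary and carries no power claim, and the detectable difference moves only from 0.13–0.20 SD to 0.12–0.16 SD. All of that stands, and it limits how much weight the point can carry.

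It can also be said that the two statements of the test are compatible, since a two-sample t-test on change satisfies both. That is fair. They need not contradict each other, but they leave the variable and the rank-test option open.

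A reader might go further than the documents allow in three ways:

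- **That the plan demonstrably gives up 15–35% of the variance.** That range needs r between 0.3 and 0.7 and equal SDs, and the documents give neither.
- **That the loss comes partly from unused 3- and 6-month scores.** The figure is ANCOVA against change score alone; the early visits contribute none of it.
- **That those scores are never used.** No analysis names them, but multiple imputation is planned and its unspecified model might draw on them.

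Finally, the remedy needs a baseline SAQ-7 that Figure 3 does not mark. The protocol says that recruitment began in August 2019, and the document is dated August 2020. If baseline was not collected, no rewording recovers it for patients already enrolled. This objection stands as a condition on the fix. It applies equally to item 7's own change score, so ANCOVA asks for no data that the plan does not already presuppose.

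**Conclusion.** The point holds as a free improvement, conditional on baseline SAQ-7 being collected as item 7 implies. The planned test is not fixed in advance, which needs no assumption to establish. The planned use of baseline is valid but less precise than it need be. The direction is certain in large samples, because the variance difference is a square. The size is not certain: 15–35% for r from 0.7 to 0.3 with equal SDs, and about 2–67% once the SD ratio may lie between 0.6 and 1.25. It would be wrong to infer bias or an invalid test.

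The 9-month/12-month conflict and the missing baseline mark come before any question of efficiency, because they decide which change is tested and whether it can be computed at all.

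**What to change.** 1. **Reconcile first.** State whether SAQ-7 is collected at baseline and correct Figure 3 or item 7 accordingly. Bring item 7's 9-month comparison into line with the 1-year endpoint and the contact schedule.
2. **Replace both SAQ-7 statements with one method.** Suggested wording: *SAQ-7 at 12 months will be compared between arms by analysis of covariance with arm and baseline SAQ-7 as covariates, in the ITT population. The adjusted mean difference will be reported with its 95% CI. If residuals are skewed, the CI will be obtained by bootstrap; the estimate will not be replaced by a rank test.*
3. **Optional.** Analyse the 3-, 6- and 12-month scores in a repeated-measures model (arm, visit, arm-by-visit, baseline and baseline-by-visit) with the 12-month contrast as the secondary result, or state that the imputation model includes the 3- and 6-month scores. Either gives those questionnaires a stated use, but the gain at 12 months is small.

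Cost: SAP wording only, if baseline SAQ-7 exists. If it does not, neither ANCOVA nor the change score can be computed, and the plan should instead state a comparison of 12-month scores with a 95% CI.
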